6.2 Data sources

The following data sources will be used to address the objectives (detailed in **Table 5**):

- Pharmacy records: intervention arms only, Arms 1-3 (i.e., not SOC arm, Arm 4)
 - Items on Prescribing Checklist, including PEP/PrEP dispensing data, age, sex, marital/relationship status, behaviors associated with HIV risk, HIV test result
 - Other services/products purchased
- Clinic records: SOC arm only
 - Items on the Clinical Encounter Form akin to those in the study's Prescribing Checklist
- Brief client surveys: all arms
 - Brief demographics
 - Whether the participant initiated PrEP and/or PEP and, if so, where
 - Whether the participant has refilled PrEP and, if so, where
 - Whether the participant is still taking PrEP/PEP as of today
 - If the participant is still taking PrEP/PEP, how many PrEP/PEP pills they swallowed in the past 7 days
 - PrEP adherence
 - Select HIV risk behavior questions

- Extended client survey: all arms
 - Extended demographics
 - Alcohol use
 - Sexual and mental health
 - HIV risk behaviors
 - Fertility
 - Social harm
 - Acceptability of pharmacy model in which they received PrEP/PEP services
 - Quality of care perceptions Fidelity of services received
 - Willingness to pay
- Provider surveys: all arms
 - Provider demographics
 - Acceptability of pharmacy-delivered PrEP/PEP
 - Feasibility of pharmacy-delivered PrEP/PEP
 - Self-efficacy to delivery PrEP/PEP services at pharmacies
 - Organizational Readiness for Change (ORIC)
 - Willingness to charge
- Client in-depth interviews: all arms
 - Model acceptability
 - Model appropriateness
 - Acceptability of modifications
 - Appropriateness of modifications
- Provider in-depth interviews: all arms
 - Acceptability
 - Feasibility
- Technical assistance (TA) reports
 - Adaptations

Data from the Maisha Meds application on PrEP/PEP delivery/dispensing, survey data, audio files from interviews, and interview transcripts will be stored on secure electronic platforms that meet all data security requirements (e.g., REDCap, Dedoose). Table 5 below summarizes the outcomes and data sources.

Table 5. Data sources

PRIMARY/ SECONDARY	OUTCOME	TIMING	DATA SOURCE
Primary	PrEP initiation	By 60 days	Brief client survey Pharmacy records* Clinic records*
	PrEP continuation	By 60 days	
Secondary	PrEP initiation	By 270 days	
	Any PrEP continuation	By 270 days	
	At least 2 PrEP refills	By 270 days	
	Any stopping and restarting PrEP (i.e., PrEP reinitiation)	By 60 and 270 days	

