To address potentially large variability in pharmacies, a **sensitivity analysis** will be conducted removing extreme outlier pharmacies to evaluate how the primary results are impacted. To address difference in when participants were reached for follow-up, another **sensitivity analysis** will be conducted that restricts follow-up data to just include those within 30 days (+/-) of their scheduled follow-up visit (the primary analysis will not restrict timing of follow-up data). An additional **sensitivity analysis** will use non-parametric permutation testing to understand the robustness of the findings of the main analysis. To account for possible imbalances across study arms, a common challenge in cluster-randomized trials, we will perform **sensitivity analyses** repeating the analyses with adjustment for pharmacy-level factors considered to be strongly predictive of PrEP initiation and continuation. Finally, a **sensitivity analysis** will be conducted repeating the primary analysis with adjustment for pharmacy-level average time to survey completion to account for delays in survey completion allowing for additional time to engage with PrEP and PEP.

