In addition, **secondary analyses** for both PrEP initiation and PrEP continuation with 60 days among the clients in the three intervention arms will be performed to compare each of the three intervention arms to each other. The approaches will be identical to that described in Sections 7.5.1.1, with the caveat that the outcome (PrEP initiation or PrEP continuation) will be computed from the pharmacy records, which is available for all three intervention arms and will be a more complete data source than the 60-day follow-up survey. Because the pharmacy data precisely reflects the day initiation or refill takes place, the computation will use a cutoff of exactly 60 days from initial pharmacy-based screening.

A **secondary descriptive analysis** will be performed to compare the data on PrEP initiation by 60 days and PrEP continuation by 60 days from the brief clients surveys versus clinic records

among those in the SOC arm (Arm 4). In particular, we will compare the number (1) initiating PrEP within 60 days and (2) continuing PrEP by 60 days between these two data sources. A similar analysis will be performed for the three intervention arms to compare the number of PrEP initiations and continuations based on the brief client surveys versus the pharmacy records.

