7.7 Post-unblinding update: December 16, 2025

The study team was unblinded to the results of the analysis on November 6, 2025 prior to the final DSMB meeting on November 13, 2025. The last version of this SAP, with all sections finalized with the exception of this post-unblinding update, was on November 5, 2025—prior to unblinding of any study team members. Summary statistics generated for the November DSMB meeting showed notable variability in completion of 60-day surveys across the 4 study arms. To understand the source of this heterogeneity, pharmacy data for the three intervention (i.e., non-SOC) arms were evaluated. These data indicated that a large number of individuals who did not complete the 60-day survey did in fact initiate/continue PrEP/PEP. This indicated that the planned outcome imputation approach, in which individuals who did not respond to the survey were assumed to have failed (i.e., not initiated/continued PrEP/PEP), likely did not reflect the nature of missingness. Following conversations with DSMB members and other experts, the study team decided to change the imputation approach.

The new imputation approach would impute PrEP/PEP outcomes for individuals who did not complete the survey using the proportion of PrEP/PEP initiations/continuations among individuals in the same pharmacy who did respond to the survey. Thus, if Pharmacy A enrolled 100 participants, 70 of whom responded to the survey and 14 of whom (20%) indicated they had initiated PrEP, then the PrEP initiation outcome for the 30 non-responders would be imputed as a binomial random variable with a success probability of 20%. As indicated above, evaluation of the pharmacy record data in the three intervention (i.e., non-SOC) arms indicated that the proportion of individuals who, per pharmacy records, initiated PrEP (for instance) was similar among those who did and did not complete the survey (42.8% and 40.5%, respectively). Thus, while the analysis based on the imputation procedure proposed in Section 6.7 will be reported in the main results manuscript as the pre-specified analysis, emphasis in that paper will be placed on the results from the analysis using the new imputation approach described in this paragraph, noting that this was not prespecified. We note that the decision to shift focus to this new imputation approach was made prior to seeing the results with the new imputation approach.

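### The planned comparison of self-reported PrEP use with dispensing records sets unlinked totals side by side, so survey non-response, late surveys and off-site dispensing are mixed with reporting accuracy.

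*SAP*

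**What the plan says.** Sections 3 and 7.5.1.1 take the primary outcome for each intervention arm against the referral arm from the 60-day brief client survey. Section 7.5.1.3 adds a descriptive comparison of that survey with dispensing data. For Arm 4, against clinic records: "we will compare the number (1) initiating PrEP within 60 days and (2) continuing PrEP by 60 days between these two data sources". For Arms 1-3, against pharmacy records: "A similar analysis will be performed for the three intervention arms to compare the number of PrEP initiations and continuations". Nothing further is specified about the set of clients, linkage, the date window or a measure of agreement.

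Other parts of the SAP bear on what the two totals would contain:

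- **Survey non-response.** Section 6.7 counts a missing survey outcome as not initiated or not continued.
- **Record coverage.** Section 7.5.1.3 says of the pharmacy records that they "will be a more complete data source than the 60-day follow-up survey".
- **Survey timing.** Section 7.5.1.1 states that "the primary analysis will not restrict timing of follow-up data". It also plans an adjustment for average time to survey completion "to account for delays in survey completion allowing for additional time to engage with PrEP and PEP".
- **Record timing.** For the comparisons among the three intervention arms, Section 7.5.1.3 says "the computation will use a cutoff of exactly 60 days from initial pharmacy-based screening".
- **Survey content.** Section 6.2 lists "Whether the participant initiated PrEP and/or PEP and, if so, where". It lists no date of initiation.
- **Observed completion.** Section 7.7 reports that summary statistics "showed notable variability in completion of 60-day surveys across the 4 study arms". It adds that many non-completers had initiated or continued according to pharmacy data.

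**The concern.** A reader who sees fewer self-reported than recorded initiations will tend to conclude that clients under-report, and a reader who sees equal numbers will tend to conclude that self-report is sound. Unlinked totals support neither conclusion. Three things other than reporting accuracy move the difference:

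1. Non-response lowers the survey total, because a client who was not surveyed can still appear in the records.
2. Late surveys, if accepted here as in the primary analysis, raise it, because events after day 60 can be reported.
3. Dispensing away from the recorded site raises it. Section 3 counts PrEP obtained at the pharmacy or the clinic, while each arm is compared with one kind of record only.

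At stake is how far readers can trust the self-reported primary outcome, arm by arm. Completion differed by arm, so an apparent difference in reporting between arms could arise with no misreporting at all. Section 7.5.2 carries the Section 7.5.1.3 analyses over to the secondary outcomes where appropriate, so the same problem would recur there.

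**Working it through.** **Inputs**

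- Planned 60-day survey completion 75%, and initiation among completers 80% (Section 4.5).
- Record-based PrEP initiation in Arms 1-3: 42.8% in survey completers and 40.5% in non-completers (Section 7.7).
- Completion by arm: not given. I show a range.
- Extra events reported because of late surveys: not given. I assume 10% and 20%.

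**Step 1: the plan's own figure.** Section 4.5 derives the enrolment target from 75% completion: 1,119 / (0.75 × 0.80) = 1,865 PrEP candidates and 2,400 / (0.75 × 0.80) = 4,000 PEP candidates, total 5,865. This agrees with the SAP. The plan itself therefore expects a quarter of enrolled clients to contribute no survey success.

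**Step 2: non-response alone.** Assume perfectly accurate self-report, every survey on day 60, records that cover all enrolled clients and capture all dispensing, and missing counted as failure. With completion r, per enrolled client:

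- survey total = r × 0.428
- record total = r × 0.428 + (1 − r) × 0.405

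At r = 0.75 the survey total is 0.321 and the record total is 0.321 + 0.25 × 0.405 = 0.422. The ratio is 0.76. Per 1,000 enrolled that is 321 against 422, a 24% shortfall with no reporting error.

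| Completion r | Survey | Records | Ratio | Apparent shortfall |
|---|---|---|---|---|
| 60% (assumed) | 0.257 | 0.419 | 0.61 | 39% |
| 75% (planned) | 0.321 | 0.422 | 0.76 | 24% |
| 90% (assumed) | 0.385 | 0.426 | 0.91 | 9.5% |

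Between arms at 60% and 90%, the ratios differ by a factor of 0.613 / 0.905 = 0.68. One arm would appear to report about one third less than the other.

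**Step 3: late surveys.** Let events after day 60 but before the survey add a fraction L to the responders' total, with records cut at 60 days. The ratio becomes r × 0.428 × (1 + L) divided by the record total.

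- At 75% completion: 0.84 for L = 10% and 0.91 for L = 20%.
- At 90% completion: 0.995 for L = 10% and 1.09 for L = 20%.

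The two effects cancel at L of about 31% when completion is 75% and about 10% when it is 90%. A ratio near 1 can therefore arise without the two sources having been shown to agree for any client. Dispensing at another site acts in the same direction as L. The SAP gives no figure for it.

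**Step 4: the linked comparison.** Among responders, with records counted to each client's survey date and both sources limited to the same site, accurate self-report gives a ratio of 1.00 at any completion rate, provided that the records are complete for that site.

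**The case against.** The strongest case on the other side has four parts.

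**The mismatch is not written down in full.** Section 7.5.1.3 describes both sources as within or by 60 days. The unrestricted survey timing is stated for the primary analysis, and the exact 60-day cutoff for the comparisons among intervention arms. A reader might infer that the SAP fixes a comparison of surveys at any date with records of all clients to day 60. It does not say so. It leaves client set and dates open, and no cutoff rule is given for clinic records. This stands, and the effect of late surveys is therefore conditional.

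**The table is not called a validity test.** It is described as descriptive. The total difference between the analysed count and the dispensing count, for all reasons together, is a fair thing to report, which is why the totals should stay. But no other planned analysis sets self-report against dispensing, so this table will be read for that purpose.

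**Section 7.7 changes the imputation.** If survey totals used the new within-pharmacy imputation, the expected ratio on the pooled Section 7.7 rates would be 0.428 / 0.422 = 1.01 at 75% completion, 1.02 at 60% and 1.005 at 90%. The non-response effect would nearly vanish in Arms 1-3. The SAP does not say that the new imputation applies here. If it did, the total would include simulated answers, which cannot test reporting accuracy.

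**The team already knows about non-response and lateness.** Section 7.7 splits pharmacy records by survey status, and Section 7.5.1.1 plans two sensitivity analyses on timing. Neither compares a client's own answer with that client's record, and the Section 7.7 split does not cover Arm 4.

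**Conclusion.** The point holds as a weakness of a descriptive table. As written, the comparison cannot separate reporting accuracy from survey completion, survey timing and place of dispensing. Under the Section 6.7 rule, non-response alone gives an apparent shortfall of about 24% at planned completion.

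That figure rests on the pooled Section 7.7 rates for PrEP initiation in Arms 1-3, on records that cover all enrolled clients and capture all dispensing, and on surveys done on time. Nothing in the SAP gives the corresponding figures for Arm 4 or for continuation. The 39% and 9.5% are illustrations at assumed completion rates. The SAP says that completion differed by arm but not by how much.

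A reader might infer that the primary estimate is changed by this table, that self-report is in fact inaccurate, or that one arm truly reports a third less. The SAP supports none of these: the table feeds no model, and the calculation assumes no misreporting throughout.

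**What to change.** Keep the totals, and add to Section 7.5.1.3 an agreement table built as follows:

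- Include clients who completed the 60-day survey, linked by person to their records.
- Count record events up to each client's own survey date.
- Limit both sources to the matching dispensing site: pharmacy in Arms 1-3, clinic in Arm 4. The survey already asks where PrEP was initiated and refilled.
- Use observed survey answers, not imputed ones.
- Report by arm, for initiation and for continuation, the percentage of record-confirmed clients who self-report the event and the percentage of self-reported events found in the records.
- State beside the totals the client set, the date window and the imputation rule used, and survey completion by arm.

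Section 7.7 shows that pharmacy records can be split by survey status in Arms 1-3, so the table is feasible there. In Arm 4, do it as far as clinic records can be linked, and state the linkage rate. The cost is a short SAP addition and a little extra analysis, with no new data collection. The downside is that linkage in Arm 4 may be incomplete, which would limit what the table can show for that arm. Because the team is already unblinded, the addition should be dated and labelled as made after unblinding.

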7.5.2 Secondary and tertiary outcomes

The analysis of the secondary outcomes of PrEP initiation within 270 days, any PrEP continuation within 270 days, at least 2 PrEP refills, any stopping and restarting PrEP, PEP initiation, PEP-to-PrEP transition, recurrent PEP use, PrEP/PEP initiation, PrEP/PEP continuation, PrEP adherence and the tertiary outcome of follow-up HIV testing will be similar to those described in Sections 7.5.1.1. Furthermore, the secondary analyses proposed in Section 7.5.1.3 will be performed for these outcomes (as appropriate for the outcome), with the exception of the secondary analysis investigating interactions. For the analysis of PrEP initiation with 270 days, the sensitivity analysis described in Section 6.7, in which PrEP initiation at 60 days is used to impute missing PrEP initiation at 270 days, will be performed.

For the exploratory outcome of PrEP coverage, descriptive statistics in each arm will be provided.

The tertiary outcomes (including acceptability, appropriateness, willingness to pay/charge, feasibility, and adaptations) will be summarized using descriptive statistics when assessed quantitatively and analyzed using a combination of inductive and deductive approaches (e.g., thematic content analysis) when assessed qualitatively. Similarly, the HIV risk behavior outcomes will be analyzed descriptively. No formal statistical comparisons will be performed for these tertiary outcomes.

7.6 Safety

7.6.1 HIV seroconversion

Seroconversion will be determined by local HIV testing guidelines. A listing of participants who seroconvert will be maintained.

7.7 Post-unblinding update: December 16, 2025

The study team was unblinded to the results of the analysis on November 6, 2025 prior to the final DSMB meeting on November 13, 2025. The last version of this SAP, with all sections finalized with the exception of this post-unblinding update, was on November 5, 2025—prior to unblinding of any study team members. Summary statistics generated for the November DSMB meeting showed notable variability in completion of 60-day surveys across the 4 study arms. To understand the source of this heterogeneity, pharmacy data for the three intervention (i.e., non-SOC) arms were evaluated. These data indicated that a large number of individuals who did not complete the 60-day survey did in fact initiate/continue PrEP/PEP. This indicated that the planned outcome imputation approach, in which individuals who did not respond to the survey were assumed to have failed (i.e., not initiated/continued PrEP/PEP), likely did not reflect the nature of missingness. Following conversations with DSMB members and other experts, the study team decided to change the imputation approach.

The new imputation approach would impute PrEP/PEP outcomes for individuals who did not complete the survey using the proportion of PrEP/PEP initiations/continuations among individuals in the same pharmacy who did respond to the survey. Thus, if Pharmacy A enrolled 100 participants, 70 of whom responded to the survey and 14 of whom (20%) indicated they had initiated PrEP, then the PrEP initiation outcome for the 30 non-responders would be imputed as a binomial random variable with a success probability of 20%. As indicated above, evaluation of the pharmacy record data in the three intervention (i.e., non-SOC) arms indicated that the proportion of individuals who, per pharmacy records, initiated PrEP (for instance) was similar among those who did and did not complete the survey (42.8% and 40.5%, respectively). Thus, while the analysis based on the imputation procedure proposed in Section 6.7 will be reported in the main results manuscript as the pre-specified analysis, emphasis in that paper will be placed on the results from the analysis using the new imputation approach described in this paragraph, noting that this was not prespecified. We note that the decision to shift focus to this new imputation approach was made prior to seeing the results with the new imputation approach.

Finally, based on discussions regarding the policy impact of the results of this study, the study team decided to include all PrEP initiations, even among those who had previously been dispensed PEP, and vice versa. All of these decisions were made prior to the study team seeing the results with these changes incorporated.

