In particular, to estimate power, it was assumed that the average pharmacy flow was the same across the four arms; there is no a priori reason to assume otherwise. We further assumed a coefficient of variation (CV) of 0.25. The coefficient of variation characterizes the variability in number of PrEP initiations (relative to pharmacy size) across pharmacies. While this is difficult to know ahead of time, it is typically <0.25 (Hayes and Bennett, *IJE*, 1999). A CV of 0.25 would roughly correspond to a situation where, for example, the average number of PrEP initiations was 20/pharmacy, and 95% of pharmacies had between 10 and 30 initiations (assuming equal flow across pharmacies); this seems to be a reasonable degree of variability in our setting. Given that the analyses will include comparisons of Arms 1, 2, and 3 vs. 4, we used a Bonferroni correction to our alpha level (two-sided alpha = 0.05/3) for the PrEP 60-day initiation/continuation outcomes and the combined PrEP/PEP outcomes (primary and key secondary outcomes).

Based on the hypothesized number of PrEP/PEP initiations and continuations in **Table 3**, we estimated the power would be very high for comparing Arms 2 and 3 to Arm 4 for PrEP initiation

and continuation (primary outcomes) and the combined PrEP/PEP initiation and continuation outcomes (key secondary outcomes; **Table 4**). For the Arm 1 vs. Arm 4 comparisons, the power is estimated to be 80% for PrEP initiation (as designed), 100% for the combined PrEP/PEP initiation outcome, and lower for the continuation outcomes.

→ **Primary outcome assessment will be completed after a total of 1,119 PrEP initiations are achieved. A study duration of 20 months of implementation is targeted.**

Table 3: Number of PrEP, PEP, and PrEP/PEP initiations and continuations per pharmacy (k=15/arm, k=60 total) for >80% power in our PrEP outcomes of interest

	1: Client-sustained	2: Implementor-sustained	3: HTS supported	4: Referral (SOC)	TOTAL (across 60 pharms)
PrEP initiations	16.13	22.18	26.21	10.08	1,119
PEP initiations	32	48	64	16	2,400
Total PrEP/PEP initiations	48.13	70.18	90.21	26.08	3,519
PrEP continuations	8.06 (50% of initiations)	15.52 (70% of initiations)	20.97 (80% of initiations)	6.05 (60% of initiations)	759
PEP continuations	4.34 (13.6% of initiations)	9.12 (19.0% of initiations)	13.90 (21.7% of initiations)	2.61 (16.3% of initiations)	450

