Total PrEP/PEP continuations	12.40	24.64	34.87	8.66	1,209

Table 4: Estimated power for PrEP initiation and continuation and the combined PrEP/PEP initiation and continuation outcomes

	Arm 1 vs. Arm 4	Arm 2 vs. Arm 4	Arm 3 vs. Arm 4
PrEP initiations	80%	100%	100%
PrEP continuations	23%	100%	100%
Total PrEP/PEP initiations	100%	100%	100%
Total PrEP/PEP continuations	48%	100%	100%

Sample sizes for other aspects of the study (e.g., extended surveys, provider surveys, costing data, IDIs), were chosen based on feasibility and ability to obtain a representative sample. The extended client surveys will include 1,340 participants across the four arms. One provider and/or HTS counselor from each pharmacy will be asked to participate in the provider survey at baseline, 60 days, and 270 days post-launch of PrEP/PEP service delivery at their pharmacy. IDIs will be conducted with up to 88 PrEP and 60 PEP candidates (with product candidacy determined by providers at enrollment following an HIV risk assessment, medical safety assessment, and counseling session). We will also interview 40 pharmacy providers, 15 HTS counselors (supporting Arm 3 pharmacies), and the study's remote clinician. IDI sampling will be done using random stratified purposeful sampling, with PrEP client sampling stratified by PrEP

initiation and continuation, PEP client sampling stratified by PEP initiation and PEP-to-PrEP transition, and provider sampling stratified by pharmacy performance (high/low performer based on PrEP initiation rates relative to other pharmacies in the same arm).

In order to achieve our targeted number of PrEP (1,119) and PEP (2,400) initiations, we anticipate needing to enroll 5,865 client participants (1,865 pharmacy PrEP candidates and 4,000 pharmacy PEP candidates). This assumes that 75% of enrolled client participants will complete the brief client survey at 60 days, and of those, 80% will initiate PrEP/PEP. Combining this target with the other types of participants (60 pharmacy providers, 15 HTS counselors, 4 remote clinicians), our total enrollment target is 5,944 participants.

5 Planned Analyses

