7.4 Characteristics at enrollment

Tables will show descriptive statistics for characteristics at enrollment for all pharmacy clients and for pharmacy PrEP and pharmacy PEP candidates, with product candidacy determined by providers following HIV risk screening and counseling, with breakdowns by study arm. Similar tables will also be presented separately for those who initiated PrEP and those who initiated PEP to understand differences in demographics among those who initiated these products across the study arms.

Analysis population: Cluster-Randomized Control Trial Client Population

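### The Section 7.7 imputation uses one pooled proportion per pharmacy, so its counts are unbiased only if survey response is unrelated to PrEP/PEP candidacy, which the SAP does not show for Arm 4

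*SAP*

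**What the plan says.** Section 6.7 counts survey non-responders as failures. Section 7.7, written after unblinding, gives the main emphasis of the results paper to a new rule that imputes them "using the proportion of PrEP/PEP initiations/continuations among individuals in the same pharmacy who did respond to the survey". In its worked example, Pharmacy A enrols 100 clients, 70 respond and 14 of those report starting PrEP; "the PrEP initiation outcome for the 30 non-responders would be imputed as a binomial random variable with a success probability of 20" per cent. One probability serves all 30, with no split by type of client.

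The enrolled clients are of two types. Section 4.5 plans for "1,865 pharmacy PrEP candidates and 4,000 pharmacy PEP candidates". Section 7.4 tabulates enrolment characteristics by candidacy and arm, "with product candidacy determined by providers following HIV risk screening and counseling". Section 4.5 also places that determination at enrolment, so candidacy is known whether or not the client later answers the survey.

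In support of the new rule, Section 7.7 reports that in the three intervention arms together, pharmacy records showed PrEP initiation in 42.8% of responders and 40.5% of non-responders. PrEP initiation is given there as an instance; no figures appear for other outcomes, for single arms or for Arm 4.

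**The concern.** Candidacy should strongly predict which product a client starts, and about two thirds of planned enrolment (4,000 / 5,865 = 68%) are PEP candidates. A pooled proportion gives both types the same probability. In a pharmacy-level count the two errors offset each other, but only if the candidacy mix is the same among non-responders as among responders. If PrEP candidates answer more often, the pooled proportion is too high for the clients it is applied to and the PrEP count is overstated; if they answer less often, it is understated.

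A pattern shared by all arms largely cancels in the rate ratios. A pattern specific to Arm 4 does not, because Arm 4 is the denominator of every primary comparison. Section 7.7 itself reports that survey completion varied notably across the four arms, and Arm 4 clients are referred to clinics instead of being served at the pharmacy. Equal response by candidacy should therefore be shown there.

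**Working it through.** **The plan's own figures.** Section 4.5 assumes that "75% of enrolled client participants will complete the brief client survey at 60 days, and of those, 80% will initiate PrEP/PEP". This reproduces the targets: 1,865 × 0.75 × 0.80 = 1,119 PrEP and 4,000 × 0.75 × 0.80 = 2,400 PEP initiations. The Section 7.7 example also reproduces: 14/70 = 20%.

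**Inputs (Table 3, per pharmacy, Arms 1/2/3/4).** PrEP initiations 16.13 / 22.18 / 26.21 / 10.08. PEP initiations 32 / 48 / 64 / 16. PEP continuations, which Section 4.5 defines as moving from PEP to PrEP, 4.34 / 9.12 / 13.90 / 2.61. Assumptions: 80% of each type start their own product, and PEP candidates start PrEP only by that transition. PrEP after PEP counts as PrEP initiation (last paragraph of 7.7).

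**Step 1: pooled and own probabilities of starting PrEP.** Candidates = initiations / 0.8. Pooled = (PrEP initiations + transitions) / all candidates. PEP candidates' own = transitions / PEP candidates.

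| | Arm 1 | Arm 2 | Arm 3 | Arm 4 |
|---|---|---|---|---|
| Pooled | 34.0% | 35.7% | 35.6% | 38.9% |
| PEP candidates' own | 10.8% | 15.2% | 17.4% | 13.1% |
| PrEP candidates' own | 80% | 80% | 80% | 80% |

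Example, Arm 4: 10.08/0.8 = 12.6 PrEP and 16/0.8 = 20 PEP candidates; pooled (10.08 + 2.61)/32.6 = 38.9%; own 2.61/20 = 13.1%.

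**Step 2: effect on the Arm 4 count.** Expected count under the rule = all candidates × pooled proportion among responders; true count = 12.69. With 85% response in PrEP and 65% in PEP candidates, responders are 12.6 × 0.85 = 10.71 and 20 × 0.65 = 13.0. PrEP starts among them are 10.71 × 0.8 + 13.0 × 0.1305 = 10.26. The proportion is 10.26/23.71 = 43.3% and the count 32.6 × 0.433 = 14.11. This is 14.11/12.69 = 1.112 times the truth, so each ratio to Arm 4 is multiplied by 1/1.112 = 0.90.

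With equal response by candidacy in Arms 1-3:

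| Arm 4 response, PrEP / PEP candidates | Arm 4 count | Rate ratios multiplied by |
|---|---|---|
| 75 / 75 | 0% | 1.00 |
| 80 / 70 | +5.5% | 0.95 |
| 85 / 65 | +11.2% | 0.90 |
| 80 / 60 | +12.0% | 0.89 |
| 70 / 80 | -5.4% | 1.06 |
| 65 / 80 | -8.2% | 1.09 |
| 65 / 85 | -10.6% | 1.12 |

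If 85/65 held in all four arms, counts would be about 10-13% too high but the ratios would move by only about 1%. PEP initiation moves the other way: at 85/65 in Arm 4 alone, and if no PrEP candidate starts PEP, its Arm 4 count is 0.89 of the truth and its ratios are multiplied by 1.12.

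**Step 3: what the reported check allows.** In the same model for Arms 1-3 pooled, 80/70 response implies PrEP initiation of 37.1% in responders and 30.1% in non-responders (gap 7.0 points); 85/65 implies 39.1% and 25.6% (gap 13.5). The observed gap is 42.8 - 40.5 = 2.3 points, corresponding to response of only about 77% against 74%. At 75% overall response the net overstatement is 0.428 / (0.75 × 0.428 + 0.25 × 0.405) - 1 = 1.4%.

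**The case against.** A reader might infer from Step 1 that the primary estimates are wrong by similar multiples, since PEP candidates receive roughly two to three times their own probability of starting PrEP and PrEP candidates less than half of theirs. The documents do not support that. The primary outcome is a count per pharmacy, so these errors cancel in expectation when response is unrelated to candidacy. The multiples are also planning values: the SAP gives no observed rates by candidacy. Against the observed 42.8%, the PrEP-candidate ratio at an 80% own rate is 0.428/0.80 = 0.535, which is not under half. Because 7.7 now counts all PrEP after PEP, the PEP candidates' true rate may exceed the planned transition share, which would narrow the contrast.

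The 42.8% against 40.5% check is real evidence. It makes 10-20 point differences in response implausible for Arms 1-3 pooled, unless other differences offset them. Scenarios that need such gaps in the intervention arms should not be relied on, and nothing in the document shows such a gap in Arm 4.

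Reliance on the rule is also limited. The Section 6.7 analysis is still reported, the new one is labelled as not prespecified, Arms 1-3 are compared with each other on pharmacy records, and Section 7.5.1.3 compares survey counts with clinic records in Arm 4. A further change after unblinding has its own cost in credibility.

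All of this stands, and it limits the point to a conditional one. It does not supply the missing evidence: the check omits Arm 4, could hide opposite patterns between arms or pharmacies, and carries no figures for continuation or PEP outcomes, which the same rule imputes.

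**Conclusion.** The point holds as an unstated and only partly tested assumption; it is not a demonstrated bias. The Section 7.7 rule needs survey response to be unrelated to candidacy within each pharmacy. For PrEP initiation in Arms 1-3 pooled, the reported check suggests a net effect of about 1-3% (1.4% at 75% response, 2.8% at 50%). For Arm 4 there is no reported evidence. A 10-20 point difference confined to that arm would lower the PrEP initiation ratios by about 5-11% or raise them by about 6-12%, depending on its direction. With equal response the bias is zero.

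These sizes rest on the Table 3 counts, 80% initiation of the candidate's own product, PEP candidates reaching PrEP only at the planned transition shares, and no difference in response by candidacy in Arms 1-3. Continuation outcomes were not quantified. The change is worth making because this analysis will carry the paper's emphasis and the stratified rule needs a weaker assumption.

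**What to change.** Impute within pharmacy and product candidacy: a non-responder's success probability is the proportion among responders of the same candidacy in the same pharmacy. Where that cell has few responders, use the same candidacy within the same arm and county group, and fix the cell-size threshold before running the analysis. Apply this to every PrEP, PEP and combined outcome imputed under Section 7.7, and report survey response by arm and candidacy.

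Because the team is already unblinded, label this as a further post-unblinding change and report it beside the current 7.7 rule and the pre-specified 6.7 analysis. At minimum it should be a sensitivity analysis.

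The cost is a paragraph in the SAP and a small change to the imputation program, using a variable already tabulated under Section 7.4. Where response is unrelated to candidacy, expected counts do not change. The downsides are sparse cells (at 75% response, a planned Arm 4 pharmacy has about 12.6 × 0.75 = 9 responding PrEP candidates and 20 × 0.75 = 15 responding PEP candidates) and one more post-unblinding analysis to disclose.
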